7.2 Inclusion Criteria

Subjects may be included in the study if they meet all of the following criteria:

- (1) The subject is between ≥ 9 and <18 years of age and weighs ≥ 20 kg.
- (2) The subject is clinically indicated to undergo a transthoracic echocardiogram.
- (3) The subject has a suboptimal non-contrast echocardiogram defined as ≥ 2 contiguous segments in any given view that cannot be visualized.
- (4) The subject is able to comply with study procedures.
- (5) A parent or legal guardian of the subject has signed and dated an informed consent form, and age-appropriate pediatric assent has been obtained where appropriate.
- (6) Post-menarchal female subjects must have a negative urine pregnancy test at screening and at pre-dose on the day of OPTISON administration.
- (7) Post-menarchal female subjects must be practicing abstinence, or be using an effective form of birth control (e.g., intrauterine device, oral contraceptives, contraceptive implants or injections, diaphragm with spermicide, cervical cap, or consort use of condom) for at least 30 days before being enrolled in the study.

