6.4.2 Primary Efficacy Analysis

Visualization of the 12 segments of the left ventricle wall in standard apical 4-chamber and 2-chamber views will be measured by the qualitative EBD visualization scale:

0 = no visualization of the LV endocardial border

1 = poor visualization

2 = fair visualization

3 = good/optimal visualization

Results for each segment will be summarized for non-contrast and OPTISON dose levels overall and by weight group ($\leq 40, > 40$ kg). A category “Visualized”, corresponding to scores 2 or 3, will also be presented. Additionally, the number of segments visualized (segments rated as “fair visualization” or “good/optimal visualization”) will be derived from the EBD score and summarized for non-contrast and OPTISON dose levels, overall and by weight group. 95% CI will be presented. A Paired t-test will be used to compare the number of segments visualized between non-contrast and each OPTISON dose level.

The number and percentage of subjects with an increase in the number of segments adequately visualized over non-contrast images will also be tabulated overall and by weight group for each OPTISON dose levels.

The Total LV EBD score, calculated as the sum of the individual scores assigned to each of the segment (range 0 to 36), will be tabulated overall and by weight group for non-contrast and each OPTISON dose level. The change from non-contrast to each OPTISON dose level will also be presented. 95% CI will be presented. A Paired t-test will be used to compare Total LV EBD scores between non-contrast and each OPTISON dose level.

A suboptimal echocardiogram is defined as ≥ 2 contiguous segments in any given view that cannot be visualized. The number and percentage of subjects with suboptimal echocardiogram will be presented for non-contrast and each OPTISON dose level, overall and by weight group.

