The change in diagnostic confidence will be derived using the same method as for change diagnostic confidence of the assessment of LV EBD and wall motion and summarized as a categorical variable by OPTISON dose level.

- LV function assessed by LVEFs, calculated using the formula: (end diastolic volume – end systolic volume)/end diastolic volume for each ventricle, will be summarized with descriptive statistics for non-contrast and OPTISON dose levels
- A composite assessment of dose suitability will be made at the subject level and results will be tabulated by OPTISON dose level. A dose will be considered suitable if it meets the following criteria:
 - (1) There is an increase in the number of segments adequately visualized over non-contrast images
 - (2) LVO peak contrast intensity assessed as medium or better
 - (3) Peak LV contrast filling to around 67% or better
 - (4) Duration of contrast enhancement ≥ 1.5 minutes.

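### A dose can be tabulated as suitable after a gain of one segment, although the enhanced echo still meets the trial's own definition of suboptimal

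*SAP*

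**What the plan says.** Protocol 7.2, inclusion criterion 3, sets the entry defect: "The subject has a suboptimal non-contrast echocardiogram defined as ≥ 2 contiguous segments in any given view that cannot be visualized".

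SAP 6.4.2 carries the same definition into the analysis ("A suboptimal echocardiogram is defined as ≥ 2 contiguous segments in any given view that cannot be visualized") and applies it after contrast: "The number and percentage of subjects with suboptimal echocardiogram will be presented for non-contrast and each OPTISON dose level". The segment count covers "Visualization of the 12 segments of the left ventricle wall in standard apical 4-chamber and 2-chamber views", each segment scored 0 to 3. The SAP says that a Visualized category "corresponding to scores 2 or 3, will also be presented".

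SAP 6.4.3 then defines suitability: "A composite assessment of dose suitability will be made at the subject level and results will be tabulated by OPTISON dose level". Four criteria must be met. The first is the only one about the border: "There is an increase in the number of segments adequately visualized over non-contrast images". The remaining three describe the contrast itself. Criterion 2 sets a floor for brightness, namely "LVO peak contrast intensity assessed as medium or better". Criterion 3 asks for filling of about 67% or more, and criterion 4 for enhancement that lasts at least 1.5 minutes.

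Protocol 12.3.2 lists the same four. Neither document sets a minimum gain, and neither refers to suboptimal status in the composite.

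**The concern.** The trial has its own standard for an inadequate echo and already derives it at each dose level, but the suitability composite does not use it. Criterion 1 is the only component that reflects the primary endpoint, and it accepts the smallest possible change. Criteria 2 to 4 describe contrast in the cavity, so they cannot make up for a weak border criterion.

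The same report could therefore count one child as suitable at a dose in the composite table and as suboptimal at that dose in the SAP 6.4.2 table. Two separate percentages would not show how many children fall into both groups. With 30 evaluable subjects (SAP 2.3), 3 such children make 3/30 = 10 percentage points.

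**Working it through.** The documents give no figure for criterion 1, so there is none to reproduce. The power table in SAP 2.3 concerns enhancement duration and plays no part here.

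**Step 1: what the text allows.** Inputs from the documents: 12 segments in two views; a segment is visualized at score 2 or 3; suboptimal means at least 2 contiguous unseen segments in a view. My assumptions: six segments per view, forming a chain (basal, mid, apical, apical, mid, basal), and unseen means score 0 or 1.

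- The smallest passing gain is 1 of 12.
- A child with k unseen segments can gain up to k − 2 and still be suboptimal. With k = 4, a gain of 2 can leave 2 contiguous unseen segments.
- With k = 2, a pure one-segment gain always clears the definition. The conflict needs k ≥ 3.
- Example: all six 4-chamber segments are unseen and all six 2-chamber segments are seen. If one basal segment becomes visible, the count goes from 6 to 7. Criterion 1 is met, and five contiguous segments are still unseen.

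Enumerating all 2^12 = 4,096 seen/unseen patterns gives the share of one-segment gains that leave the echo suboptimal:

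| Unseen at baseline | Still suboptimal | If the two apical segments are not counted as contiguous |
|---|---|---|
| 2 | 0% | 0% |
| 3 | 36% | 35% |
| 4 | 60% | 57% |
| 5 | 78% | 74% |
| 6 | 92% | 87% |
| 7 | 98% | 95% |
| 8 | 100% | 99% |

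These are shares of equally weighted patterns, not predicted patient rates.

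The SAP does not say which scores count as unable to be visualized. If only score 0 counts, a segment elsewhere that moves from 1 to 2 meets criterion 1 and leaves both score-0 segments untouched, so the conflict can then arise even with 2.

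**Step 2: how easily noise meets criterion 1.** Assume that contrast changes nothing and that each segment is misclassified (seen/unseen) independently with probability e on each of the two readings. The documents give no value for e, so 0.05 and 0.10 are illustrative. Per segment, the change is +1 or −1 with probability e(1 − e) each. The sum over 12 segments is symmetric, so P(net gain ≥ 1) = (1 − P(net = 0))/2.

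- e = 0.05: e(1 − e) = 0.0475; P(net = 0) = 0.4185; P(net gain ≥ 1) = (1 − 0.4185)/2 = 0.291.
- e = 0.10: e(1 − e) = 0.09; P(net = 0) = 0.2823; P(net gain ≥ 1) = (1 − 0.2823)/2 = 0.359.

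Under the same model, I enumerated how often a gain occurs together with conversion from suboptimal to not suboptimal:

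| True unseen run in one view | e = 0.05 | e = 0.10 |
|---|---|---|
| 2 contiguous | 6.4% | 10.0% |
| 4 contiguous | 0.6% | 2.1% |

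**Step 3: sensitivity to the noise model.** If the baseline count is instead taken as fixed and only the contrast reading flips (5-20% per segment), a net gain of at least 1 appears in about 5-7% with 2 unseen, 13-17% with 4 and 20-36% with 6. The result depends strongly on the model, but the rate rises with the number of unseen segments.

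**The case against.** The strongest reply is that most of the information will be reported anyway. SAP 6.4.2 tabulates suboptimal status for non-contrast and each dose, overall and by weight group, and SAP 6.4.5 repeats every efficacy summary by reader. The segment counts have confidence intervals and paired tests, and SAP 6.4.3 reports diagnostic usefulness. An unrepaired echo would therefore be visible. This stands. What is missing is the link between that status and the suitability result in the same child.

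The second reply is that the composite decides nothing alone. It is a descriptive secondary table in a study that tests no hypotheses. Protocol 10.2.1 bases dosage mainly on the improvement in segments, with intensity, filling and duration as supplements, and also weighs image quality, diagnostic confidence and safety. This also stands. A reader might infer that the composite percentage fixes the dose, or that the plan contradicts itself. Neither follows: no rule makes the percentage decisive, and no passage says that suitable means the entry defect is fully repaired.

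A reader might also take 29-36% as the rate at which noise makes a dose suitable. It is not. It concerns criterion 1 under assumed error rates, and all four criteria must be met. Likewise, a reader might infer that criterion 1 separates the two dose levels poorly. Nothing in the documents shows that, and no calculation here supports it.

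**Conclusion.** The point holds as a gap in the composite. A net gain of one segment meets the only border criterion, and nothing else in the composite prevents a suitable result while the echo remains suboptimal by the trial's own definition. For a pure one-segment gain this needs at least 3 unseen segments at baseline if unseen means score 0 or 1. That part rests on the text alone.

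The size is illustrative. With no true effect and 5-10% independent misclassification, noise meets criterion 1 in 29-36% of paired readings. Adding conversion out of suboptimal lowers this to about 6-10% at the 2-segment entry threshold and 0.6-2% with 4 contiguous unseen. The advantage of the stricter criterion is therefore much smaller near the entry threshold. Rates for the full composite are lower by an amount that the documents do not allow one to calculate.

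**What to change.** In SAP 6.4.3 and Table 14.2.10, keep the protocol-defined composite and add a supplementary version, by reader:

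- Criterion 1 requires both an increase in segments visualized and an enhanced echo that is not suboptimal at that dose. Criteria 2 to 4 stay unchanged. Both parts are needed: with 2 unseen segments and e = 0.05-0.10, conversion without any net gain occurs in about 2-4% of readings under the Step 2 model.
- State that a segment counts as unseen at score 0 or 1, consistent with Visualized being 2 or 3.
- Report it in all FAS subjects and, separately, in those whom that reader scored suboptimal without contrast, with both denominators shown. A child who entered on the site's assessment but is not scored suboptimal by a blinded reader then does not fail automatically.
- Report both versions next to the dosage conclusion and discuss any disagreement.

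The cost is SAP wording and one more table from variables already derived. No new data are needed. The suitable percentages in the added version will be lower.

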6.4.4 Handling of Uninterpretable Images

In the FAS analysis of the primary endpoint, the uninterpretable images will be categorized as none for contrast intensity and 0 visualization of EBD. In the secondary analyses, the uninterpretable images will be considered as 0 enhancement duration, poor for image quality, and non-diagnostic for diagnostic usefulness. Additionally, the number of uninterpretable images will be summarized by non-contrast and dose level.

6.4.5 Reader Differences

All efficacy summaries described in Section 6.4 will be presented by reader.

Data from re-read will be listed.

6.5 Safety Analysis

6.5.1 General Considerations

The safety of the intravenous administration of OPTISON in the pediatric population will be measured by the incidence of AEs, vital signs, SaO₂ by pulse oximetry, physical examination and ECG results. Safety data will be summarized overall and for each weight group (≤ 40 , > 40 kg).

6.5.2 Analysis of Adverse Events

6.5.2.1 Treatment-Emergent Adverse Events

An AE will be considered as treatment-emergent if it starts or worsens after OPTISON administration. Any AE with an onset on the day of IMP administration for which the time of onset is missing will be assumed to be treatment-emergent.

All summaries of AEs will be based on TEAEs and will be prepared by weight group (≤ 40 , > 40 kg) and overall for the Safety Population. AEs will be mapped to System Organ Class (SOC) and preferred terms using the MedDRA version 24.0. All AEs will be listed.

An overall summary of TEAEs will present the number (%) of subjects and number of events for the following events:

- TEAE
- Severe TEAE
- Serious TEAE
- TEAE considered related to IMP
- Serious TEAE considered related to IMP
- TEAE leading to discontinuation of study drug
- TEAE leading to death

The number and percentage of subjects experiencing TEAEs, and the number of events will be summarized by SOC and preferred term in alphabetical order. Summaries of TEAEs by maximum severity and TEAEs considered related to the study drug will also be presented by SOC and preferred terms.

6.5.2.2 SAEs (Including Deaths) and Adverse Events Leading to Study Drug Discontinuation

The number and percentage of subjects, with the corresponding number of events, experiencing treatment-emergent SAEs (including deaths) and adverse events leading to discontinuation of study drug will be tabulated by SOC and preferred term, overall and by weight group. Deaths, SAEs and TEAEs leading to discontinuation of study treatment will be listed.

6.5.3 Analysis of Vital Signs and Weight

6.5.3.1 Variables and Criteria Defining Abnormality

Vital sign variables are systolic blood pressure, diastolic blood pressure, heart rate, respiratory rate, and pulse oximetry. These will be measured at pre- and post-treatment time points as specified in [Table 2](#).

[Table 4](#) presents the criteria for vital sign normal limits in a pediatric population by age group for respiratory rate, heart rate, systolic blood pressure, and weight. Besides, pulse oximetry < 95% will be considered as abnormal in this study.

Table 4 Pediatric Vital Signs Normal Ranges

Age Group	Respiratory Rate	Heart Rate	Systolic Blood Pressure	Weight in kilos	Weight in pounds
School Age (6-12 yrs.)	20 – 30	70 – 110	80 – 120	20 – 42	41 – 92
Adolescent (13+ yrs.)	12 – 20	55 – 105	110 – 120	>50	>110

REF: Source: <http://www.rnceuus.com/psvt/psvtvs.html>

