6.5.3.2 Statistical Methods

The presentation of vital signs focuses on the descriptive summaries at baseline, at 10 minutes, and at 1 hour post-OPTISON administration, and the change from baseline to the 10-minute and 1-hour post-OPTISON assessments. All subjects in the safety population who have a baseline and a post-baseline assessment of vital signs will be included in the presentation of the results. Results will be presented by weight group (≤ 40 , > 40 kg) and overall.

In addition to the change from baseline results, the shifts from baseline to the post baseline visit will be summarized in tabular form for heart rate and systolic blood pressure. Subjects will be classified at baseline and the post-baseline visit in one of the following categories based on a comparison of the vital sign result to the reference range

for that vital sign parameter: below normal, normal, or above normal. A shift table will be constructed in which each subject is cross-classified based upon the reference range categories. The number and percentage of subjects in each shift table cell will be displayed. The number of subjects in the safety population missing either baseline or post-baseline vital sign information will also be presented. Results will be presented by weight group and overall. All vital signs results will be listed. Classification (below normal, normal, or above normal) will be presented in the listing for respiratory rate, heart rate, systolic blood pressure, and pulse oximetry.

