6.5.4 Analysis of ECG Parameters

6.5.4.1 Variables and Criteria Defining Abnormality

A 12-lead ECG will be measured at the various pre- and post-treatment time point ranges described in [Table 2](#). The ECGs will be characterized as normal or abnormal, and, if abnormal, whether the abnormality is clinically significant. These overall readings will be an interpretation based on ECG intervals (heart rate, PR, RR, QRS, QT, QTcF [Fridericia]). QTcF will be defined as follows:

- Fridericia's correction (QTcF): $QT_C F = QT / \sqrt[3]{RR}$
- Bazett's correction (QTcB): $QT_C B = QT / \sqrt{RR}$

Normal ranges for the observed values and change from baseline by age group are defined in [Table 5](#), [Table 6](#) and Table 7.

Table 5 Mean and Percentiles of ECG Cardiac Measures Among Pre-pubertal Children

ECG Variable	Mean (sd)	1 st %ile	5 th %ile	Median	95 th %ile	99 th %ile
Heart Rate (bpm)	83.0 (12.1)	59	65	82	104	114
RR Interval (ms)	738.5 (107.8)	526.3	576.9	731.7	923.1	1040
PR Interval (ms)	132.8 (17.3)	100	108	130	162	180
QRS Interval (ms)	80.0 (9.0)	64	70	80	96	102
QT Interval (ms)	354.7 (24.3)	300	318	352	396	416
QTc Bazett (ms)	414.0 (19.6)	367	383	414	443	460
QTc Data-derived (ms)	399 (17.3)	357.4	372	398.7	424.1	439.6
QTc Fridericia (ms)	393.2 (17.1)	353.3	366.3	392.9	419	433

Note: Pre-pubertal group (N = 1537) defined as females whose age was \leq 8 years (n = 224) and males whose age was \leq 9 years (n = 1313). Source: Child and Adolescent Psychiatry and Mental Health 2007;1:11

Table 6 Mean and Percentiles of ECG Cardiac Measures Among Pubertal Children

ECG Variable	Mean (sd)	1 st %ile	5 th %ile	Median	95 th %ile	99 th %ile
Heart Rate (bpm)	77.4 (11.8)	54	60	76	98	109
RR Interval (ms)	792.9 (121.1)	555.6	612.2	780	1000	1132
PR Interval (ms)	136.8 (18.5)	100	112	136	170	190
QRS Interval (ms)	83.0 (9.1)	68	70	80	96	106
QT Interval (ms)	368.8 (27.0.)	310	330	368	412	440
QTc Bazett (ms)	415.6 (21.3)	362	381	416	448	468
QTc Data-derived (ms)	403.9 (19.1)	357	373.3	404	433.1	450.1
QTc Fridericia (ms)	399.4 (19.0)	354.5	369.4	399.6	429	443.9

Note: Pubertal group (N = 3656) defined as females whose age was > 8 and \leq 13 years (n = 881) and males whose age was > 9 and \leq 14 years (n = 2775). Source: Child and Adolescent Psychiatry and Mental Health 2007;1:11

Table 7 Mean and Percentiles of ECG Cardiac Measures Among Post-pubertal Children

ECG Variable	Mean (sd)	1 st %ile	5 th %ile	Median	95 th %ile	99 th %ile

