6.5.4.2 Statistical Models

All subjects in the safety population who have a baseline and a post-baseline assessment of ECG data will be included in the presentation of the results. Overall ECG investigator interpretation will be categorized as normal, abnormal (Not Clinically Significant), and abnormal (Clinically Significant). Number and percentage of subjects in each category at each timepoint will be presented.

Consistent with ICH E14 guidance, ECG data will be presented both as analyses of central tendency (e.g., means, medians) and categorical analyses. ECG data will be summarized overall and by weight group (\leq 40, $>$ 40 kg).

Twelve-lead ECG data (observed values and changes from baseline) will be presented using descriptive statistics by weight group (≤ 40 , > 40 kg) and overall for each time point (baseline, 10 minutes, and 30 minutes post-dose).

In addition to the observed values and change from baseline results, the shifts from baseline to post-baseline time points will be summarized in tabular form for each ECG parameter and the overall interpretation. The overall interpretation will be based on the categories of the interpretation listed previously, while the ECG parameters will be listed based on being below normal ($< 1^{\text{st}}$ percentile), normal, or above normal ($> 99^{\text{th}}$ percentile) compared to the reference ranges in [Table 5](#), [Table 6](#) and Table 7. The number and percentage of subjects in each shift table cell will be displayed. The number of subjects who are missing either baseline or post-baseline ECG data will also be provided for each timepoint.

All ECG results will be listed including overall interpretation and status compared to normal ranges (below normal / normal / above normal).

In addition, changes from baseline in the QTc interval will be displayed according to the Committee for Medicinal Products for Human Use (CHMP) criteria (absolute QTc interval prolongation, of > 450 , > 480 , > 500 ms and change from baseline in QTc interval > 30 and > 60 ms).

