9 SUMMARY OF CHANGES

Changes from the statistical analyses planned in the protocol are summarized in the following table:

Protocol Amendment A01 Version 2.0	Changes
ITT population All subjects enrolled in the study who have available non-contrast harmonic images and OPTISON-enhanced echocardiographic images, irrespective of the quality of CE-ECHO.	For consistency with ICH E9 guidance, the efficacy population has been renamed from ITT population to Full Analysis Set. The PP Population definition has been updated to all subjects in the FAS population who do not have important protocol deviation impacting the study primary endpoint. A lack of contrast enhancement is not considered as a protocol deviation. Nevertheless, any important deviation from the Imaging Manual (e.g. wrong settings for echocardiographic imaging, standard apical 4-chamber and 2-chamber views not acquired...) will be reviewed during the Data Review Meeting and exclusion from the PP Population will be assessed.
All summary tables and data listings will be separated by dose levels.	Whenever relevant, summaries and listings will be presented by Weight group (≤ 40 , > 40 kg) and dose level.
Medications will be presented by ATC Class 1 and preferred term	Prior and concomitant medications will be tabulated by ATC Class 3 and preferred term
Primary endpoint analysis	Supportive analyses added in Section 6.4.2

Reference ranges for Vital signs	Adolescent (13+ yrs.) category added in Reference ranges table Table with reference ranges for Post Pubertal Children added
Reference ranges for ECG	Table with reference ranges for Post Pubertal Children added

Any deviations from the statistical analysis outlined in the SAP will be described, and reasons for the deviations listed, in the final Clinical Study Report.

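### SAP Table 4 and SAP Tables 5 to 7 set conflicting lower limits for heart rate, and the adolescent systolic band is 10 mmHg wide, which adds noise to the vital-sign shift table

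*SAP*

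**What the plan says.** SAP 6.5.3.1, Table 4, has two age rows that apply to this trial, which enrols from age 9 to under 18.

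- "School Age (6-12 yrs": heart rate 70 to 110 bpm, systolic pressure 80 to 120 mmHg.
- "Adolescent (13+ yrs": heart rate 55 to 105 bpm, systolic pressure 110 to 120 mmHg.

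The second row is a SAP addition. SAP section 9 records it as "Adolescent (13+ yrs.) category added in Reference ranges table", and the protocol's own table stops at ages 6 to 12. Section 9 does not explain the width of the new systolic band.

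SAP 6.5.3.2 uses these limits to class each child as below normal, normal or above normal at baseline and afterwards. The shifts "will be summarized in tabular form for heart rate and systolic blood pressure". The same classification "will be presented in the listing for respiratory rate, heart rate, systolic blood pressure, and pulse oximetry".

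ECG heart rate is handled differently. SAP 6.5.4.2 describes the ECG shift table with the words "while the ECG parameters will be listed based on being below normal", normal or above normal, with cuts at the 1st and 99th percentiles of Tables 5 to 7. The note to Table 6 begins "Pubertal group (N = 3656) defined as females whose age was > 8 and" and runs to age 13 for girls; for boys the group is above 9 up to 14. It therefore covers the trial's girls aged 9 to 12 and boys aged 10 to 12.

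**The concern.** One parameter has two definitions of normal in the same safety report. Vital signs and the 12-lead ECG are both recorded at baseline and at 10 minutes (SAP Table 2). An 11-year-old at 60 bpm would be below normal in Table 14.3.3.2 and normal in Table 14.3.4.2, and nothing in the SAP explains why.

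The systolic limits jump with age. At a 13th birthday the lower limit rises from 80 to 110 mmHg while the upper limit stays at 120.

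Heart rate and systolic pressure are the only vital signs given shift tables, and the trial has no untreated arm from which a background rate of category changes could be subtracted. A limit that cuts through the middle of the ordinary range makes children cross it by normal variation, and real shifts are harder to pick out.

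**Working it through.** **Check of the SAP's own percentiles.** Heart rate should equal 60000 divided by RR in ms. In Table 6, 60000/1000 = 60.0 (5th percentile, printed 60) and 60000/612.2 = 98.0 (95th, printed 98). The 1st and 99th come out at 60000/1132 = 53.0 (printed 54) and 60000/555.6 = 108.0 (printed 109). In Table 7, 60000/1250 = 48.0 and 60000/1153.8 = 52.0, both as printed. The tables are consistent to within about 1 bpm.

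**Limits side by side (bpm).**

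| Children | Table 4 | 1st to 99th percentile, Tables 5 to 7 |
|---|---|---|
| Boys aged 9 (pre-pubertal) | 70–110 | 59–114 |
| Girls 9–12, boys 10–12 (pubertal) | 70–110 | 54–109 |
| Girls 13, boys 13–14 (pubertal) | 55–105 | 54–109 |
| Older adolescents (post-pubertal) | 55–105 | 48–102 |

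**Share of each reference group below the Table 4 limit.** Formula: Φ((limit − mean)/SD), with mean and SD from Tables 5 to 7. The second figure interpolates between the printed percentiles on the z scale.

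- Pubertal against 70: Φ((70 − 77.4)/11.8) = Φ(−0.627) = 26.5%; interpolated 26.9%.
- Pre-pubertal against 70: Φ((70 − 83.0)/12.1) = Φ(−1.074) = 14.1%; interpolated 12.3%. In this trial that is only 9-year-old boys.
- Post-pubertal against 55: Φ((55 − 70.8)/11.4) = Φ(−1.386) = 8.3%; interpolated 8.5%.
- Pubertal against 55: Φ((55 − 77.4)/11.8) = Φ(−1.898) = 2.9%; interpolated 1.3%.

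The percentile limits flag about 2% by construction.

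**Heart-rate category changes with no drug effect.** Baseline and post-dose values were simulated as bivariate normal with the Table 6 mean and SD. The documents give no baseline-to-post correlation; 0.6 to 0.9 is assumed. With 70 to 110, 12% to 24% of pubertal children change category. With 54 to 109, 2% to 4% do. For the post-pubertal group the figures are about 5% to 11% with 55 to 105 and 2% to 4% with 48 to 102.

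**Adolescent systolic pressure.** The documents give no mean or SD, so everything here is assumed: normal distribution, mean 105 to 115, SD 8 to 12. The share inside 110 to 120 is Φ((120 − mean)/SD) − Φ((110 − mean)/SD).

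| Mean | SD 8 | SD 10 | SD 12 |
|---|---|---|---|
| 105 | 23.6% | 24.2% | 23.3% |
| 110 | 39.4% | 34.1% | 29.8% |
| 115 | 46.8% | 38.3% | 32.3% |

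The range is 23% to 47%. Over the same grid, 66% to 97% would lie inside 80 to 120.

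For category changes with no effect, assuming mean 110 to 115, between-child SD 10 and within-child SD 5, simulation gives 32% to 35% with 110 to 120 and 14% to 18% with 80 to 120.

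**The case against.** The shift table is not the main vital-sign analysis. SAP 6.5.3.2 puts descriptive summaries and change from baseline first and adds the shifts to them. Change from baseline does not use Table 4, every result is listed, and protocol 10.3.1 makes a clinically significant worsening an adverse event whatever the range says. This stands.

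Baseline and post-baseline values meet the same limits, so a child who is usually at 65 bpm appears as below normal both times and not as a shift. The 26.5% is a labelling rate, not a rate of false shifts; the no-effect simulation addresses shifts, and it needs an assumed correlation. This also stands.

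The systolic figures rest wholly on assumed inputs, and part of the category change would arise from any cut at 120, as the 14% to 18% shows. Table 4 cites a source that cannot be checked here.

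The percentile tables are not an ideal standard either. The pubertal group is 2775 boys and 881 girls, and it is not a cardiac population.

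A reader might infer that the limits could create or hide a safety signal, or that most shifts will be artefact. The documents do not support either: a real change remains visible in the continuous summaries, the listings and the adverse events, and the share of shifts due to ordinary variation cannot be fixed without data that the documents lack. None of this explains why one heart rate is judged by two standards.

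**Conclusion.** The contradiction in heart rate is in the text and needs no outside assumption. It lies at the lower limit and mainly at ages 9 to 12, where 70 stands against 54 and 26.5% of the SAP's own pubertal reference group falls below 70. It is small in adolescents, and the upper limits nearly agree (110 against 109, 105 against 102). With the 30 evaluable subjects now planned and an unknown age mix, an assumed 5 to 15 children aged 9 to 12 would give about 1 to 4 labelled low at baseline (5 × 0.265 = 1.3; 15 × 0.265 = 4.0), if they resemble the reference group.

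The 10 mmHg adolescent systolic band and the jump at 13 are also in the text, but how many children they mislabel is assumption, not fact.

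The consequence is noise and dilution in a supplementary descriptive table, without a consistent direction. The point is worth correcting because the remedy is nearly free.

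**What to change.** Before database lock:

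1. Classify vital-sign heart rate by the 1st and 99th percentiles of SAP Tables 5 to 7, with the same age and sex groups as for ECG heart rate, in both the shift table and the listing. The two safety tables then use one standard.
2. Check the adolescent systolic band against its cited source and reconcile it with the 6-to-12 band, giving the reason for whatever is kept. No limit is proposed here, because the documents contain nothing from which to derive one.
3. State that systolic pressure will be interpreted from change from baseline, with the shift table as support.

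The cost is SAP wording and a change to one lookup in the programs. The drawback is that the heart-rate reference is not a cardiac population; a footnote to the table should say so.
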